RESEARCH PROTOCOL TEMPLATE INVESTIGATOR INITIATED TREATMENT TRIALS

Title of Project: Utility of three-dimensional transesophageal echocardiography in right ventricular function assessment in surgical aortic valve replacement, mini-sternotomy aortic valve replacement, and transcatheter aortic valve replacement

Principal Investigator: [name]; Department of Anesthesia

Co-Investigators: [name]; Department of Anesthesia
[name]; Department of Anesthesia
[name]; Department of Anesthesia
[name], DO; Department of Anesthesia
[name], DO; Department of Anesthesia
[name]; Department of Medicine
[name]; Medical Student

Abstract

Objective: Right ventricular (RV) function is known to be a critical factor to determine postoperative outcome in cardiac surgery, and echocardiography plays an important role in RV function assessment.¹⁻² In the previous studies, RV function was reported to be more reduced in surgical aortic valve replacement (SAVR) than transcatheter aortic valve replacement (TAVR), but its assessment was performed by 2-dimensional echocardiography.^{3,4} On the other hand, three-dimensional (3D) echocardiography has been the gold standard to assess RV systolic function (EF: ejection fraction), and its intraoperative use is getting more useful in cardiac surgery given recent technological advance in echocardiography machines.¹ However, reality is that we tend to determine RV function based on subjective information or traditional RV function indices, mostly due to unfamiliarity of 3D technique.

In this study, we plan to evaluate intraoperative RV function assessment by 3D transesophageal echocardiography (TEE). We will compare 3D RV EF with other traditional RV function indices ((RV fractional area change (FAC) and tricuspid annular plane systolic excursion (TAPSE)) in SAVR, mini-sternotomy AVR (mini AVR), and TAVR.

A. Specific Aims

1. RV function assessment pre, post cardiopulmonary bypass (CPB), and post chest closure

In 3 arms (arm 1: surgical AVR, arm 2: mini AVR, arm 3: TAVR), baseline pre CPB RV function assessments done after induction of general anesthesia. Post CPB RV function assessment after weaning off CPB and after chest closure is done in the same way as baseline pre CPB RV function assessment. RV function assessment to include 3D RV EF, RV FAC, and TAPSE). In arm 3: TAVR, baseline RV function assessments done

after induction of general anesthesia. Post TAVR RV assessment is done in the same way as baseline RV function assessment.

2. **Compare 3D RV EF between SAVR, mini AVR, TAVR.**

See Table below for the timing of assessment

	SAVR	Mini AVR	TAVR
Baseline RV (T#1)	Post induction		
Post valve deployment RV (T#2)	Post CPB		Post valve deployment
Post chest closure RV (T#3)	Post chest closure or before extubation		

B. Background and Significance

The importance of postoperative RV function after cardiac surgery has been recognized for more than 30 years, but its assessment has been challenging due to the unique anatomy, physiology, and its position. The RV is pyramid shape, its contraction consists mostly of longitudinal movement, and is less accessible due to its retrosternal position. Thus, RV function assessment has been comprehensive utilizing RV size, RIMP, RV FAC, S', TAPSE, surgeons' "eyeball" impression. With emergence of 3D echocardiography technology, 3D-derived RV EF is the most accurate echocardiographic measure of global RV function¹ Previous study^{3,4} has shown that RV function is more reduced in SAVR than TAVR however their RV assessment was mostly with 2-dimensional echocardiography. This study will be the first study to utilize 3D echocardiography for RV function assessment for SAVR, mini AVR, and TAVR.

C. Preliminary Studies/Progress Report

N/A

D. Research Design and Methods

Design: Prospective clinical trial at single-center tertiary academic hospital.

Participants: Aortic valve surgery patients

Arm 1 (SAVR)

Arm 2 (mini AVR)

Arm 3: (TAVR)

Primary outcome: 3D RV EF

Secondary outcome: Traditional RV function indices (RVFAC and TAPSE)

[figure not shown]
Anesthesia methods: general anesthesia with endotracheal intubation, arterial line, central venous line, pulmonary artery catheter (not for TAVR), TEE.

Anesthesia will be general anesthesia with endotracheal tube, pre-induction arterial line, central venous line, pulmonary arterial catheter (not for TAVR), and TEE; all of which are within standard care, and nothing specific to this study. Choice of the medication including inotropes and vasopressors, and intervention such as transfusion and fluid management will be at each anesthesiologist's discretion.

Measurements:

Training for acquisition of images will be provided by GE representatives to the Cardiac Anesthesiologists. All images will be saved in the operating room and transmitted to server for permanent catalogue. A single investigator will review all images and make the measurements described below.

[figure not shown]
3D RV EF will be acquired using the GE software package on the GE vivid e95 TEE machine. Firstly, TEE midesophageal 4 chamber view (ME 4CV) with RV focus is acquired with 4D mode, then 4D RVQ software is activated on that image, align anatomical landmark as directed, and the software will calculate the 3D RV EF automatically.

[figure not shown]
The following TEE measurements were then obtained over three consecutive beats using TEE 4CV with RV focus, and a single cardiac cycle from these image sets was then used to calculate post-hoc measures of RV function including TAPSE and RVFAC

RV FAC will be calculated from ME 4CV with RV focus.

FAC = $100 \times \frac{\text{end-diastolic area (Area ED)} - \text{end-systolic area (Area ES)}}{\text{end-diastolic area}}$. The endocardial border is traced in apical 4-chamber views from the tricuspid annulus along the free wall to the apex, then back to the annulus, along the interventricular septum at end-diastole (ED) and end-systole (ES). Trabeculation, tricuspid leaflets, and chords are included in the chamber.

TAPSE will be measured by TAPSE measurements obtained via the ME 4CV using anatomic M-mode (AMM TAPSE). The anatomic M-mode measurements were completed by placing the cursor on the lateral tricuspid annulus and the angle was adjusted such that the angle of measure was directed toward the apex.

E. Statistical Methods

Statistical analysis

Summary statistics will be reported for demographic and clinical data for each group. Similarly, variables are presented as mean \pm SD and median (IQR), when indicated. Categorical data are presented as frequencies and percentages according to the group. Demographic data will be analyzed using the independent t-test, and the Mann–Whitney U test will be used for nominal variables. RV echocardiographic indices will be analyzed using the Mann–Whitney U test (2 groups) or the analysis of covariance (ANCOVA) and pos-hoc pairwise comparisons with Bonferroni correction. For ANCOVA of % change (Timing #3 from #1) in RV indices, covariates included age, gender, norepinephrine equivalent (NE equiv) at Timing #3, CVP at Timing #1, and each RV index at the baseline (Timing #1). Univariate or multivariable logistic regression models were used to assess the association between each echocardiographic index and in-hospital MACCEs. Correlations between continuous variables will be assessed using Pearson's or Spearman's rank correlation tests. Statistical significance is set at $p < 0.05$. All statistical analyses are performed using R version 4.5.1 (The R Foundation for Statistical Computing).

Power analysis

Changes in RV echocardiographic measurements were used to calculate the required sample size, based on a study by Kempny et al.[4] Kempny et al. reported %change of right ventricular strain of - 25.2 (SAVR) and - 20.0 (TAVR) before and after the

procedure, respectively. With the criterion for significance (alpha) set at 0.05 and 80% power for a Mann–Whitney U test, we obtained a sample size of 22 patients per group. The rationale for using RV strain for power analysis is as follows; Sample size calculations for RV strain, RVFAC, and TAPSE provided 22, 7, and 15, respectively. Thus, we decided to use the strictest sample size calculation.

F. Gender/Minority/Pediatric Inclusion for Research

Adult patients over 18 years old are included. Any gender and race patients are included.

G. Human Subjects

1. Inclusion criteria: Adult patients over 18 years old who have mitral valve procedures
Exclusion criteria: patients' refusal, suboptimal echocardiography data
2. Sources of research material in the form of specimens, records or data.
Echocardiography data, medical information in EPIC
3. Plans for recruitment and consent procedures to be followed.
Phone consent will be done in preoperative or actual consent will be obtained in preoperative holding area.
4. Risks and assess likelihood and seriousness. No research related risks are anticipated because TEE measurements are standard care
5. Procedures for protecting against or minimizing potential risks. N/A
6. Potential benefits and importance to the subjects and others. Patients may benefit from more detailed clinical data than usual by joining this study. Especially, training cardiac anesthesiologists for 3D TEE will help for obtaining more clinical data which might be leading to necessary intervention.
7. Why risks are reasonable in relation to benefits. No research related risks are anticipated, and possible benefits are higher (described in 6)

H. Data and Safety Monitoring Plan

All protocols that pose greater than minimal risk must have a Data and Safety Monitoring Plan (see DHSP policy G 616 "Independent Monitoring of Investigator-Initiated Clinical Trials.")

1. Describe the Data and Safety Monitoring Plan (DSMP)
We will report to IRB if we should come across research related complications

2. If applicable, describe the Data and Safety Monitoring Board (DSMB) that will be responsible for monitoring the study. Indicate Chair, members, areas of expertise, frequency of meetings, distribution of reports.

N/A

I. Literature Cited

1. Lang RM, Badano LP, Mor-Avi V, Afilalo J, Armstrong A, Ernande L,

et al. Recommendations for cardiac chamber quantification by echocardiography in adults: an update from the American Society of Echocardiography and the European Association of Cardiovascular Imaging. J Am Soc Echocardiogr 2015;28(January (1)). 1–39.e14.

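### Nothing limits the arms to isolated valve replacement and the ANCOVA has no term for a concomitant operation, so Aim 2 can count added surgery as an effect of approach

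*Combined protocol and SAP*

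**What the plan says.** Aim 2 (Section A) is to "Compare 3D RV EF between SAVR, mini AVR, TAVR", and Section D makes 3D RV EF the primary outcome. The three arms are named by approach alone: surgical, mini-sternotomy and transcatheter replacement. No randomisation is described.

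The population line in Section D reads "Participants: Aortic valve surgery patients". Section G.1 gives the formal criteria: "Inclusion criteria: Adult patients over 18 years old who have mitral valve procedures", followed by "Exclusion criteria: patients' refusal, suboptimal echocardiography data". The first of these conflicts with the title, the aims and the arms, which all concern the aortic valve. Nowhere does the written text confine enrolment to isolated replacement, or exclude, stratify by or record a concomitant operation.

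Section E allows a Mann–Whitney test for two groups, which has no covariates, or an ANCOVA. For percentage change from Timing #1 to Timing #3 the ANCOVA "covariates included age, gender, norepinephrine equivalent (NE equiv) at Timing #3, CVP at Timing #1, and each RV index at the baseline (Timing #1"). Concomitant procedure, bypass time and cross-clamp time are absent.

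**The concern.** A second operation done with the valve replacement falls between the baseline measurement and the post-bypass and post-closure measurements. It changes the procedure whose effect is being compared, so it is more than a baseline difference between patients. If it occurs at different rates across arms and also lowers RV function, part of the between-arm difference in 3D RV EF belongs to the added surgery.

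The likely direction matters. Section B already expects RV function to be more reduced after SAVR than after TAVR. If combined operations concentrate in the full-sternotomy arm, the bias runs the same way, and a positive Aim 2 result could not be told apart from a case-mix effect.

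**Working it through.** **1. Text check.** Three places could block a combined operation: the population line (D), the criteria (G.1) and the covariate list (E). None does. The arm labels limit the study to valve replacement, so repair alone is outside it, but replacement plus another operation is admitted.

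**2. The plan's own figure.** Section E gives 22 per group for a Mann–Whitney test at alpha 0.05 and 80% power, from RV-strain changes of −25.2 and −20.0, a difference of 5.2 points. No SD is stated, so 22 cannot be reproduced directly. It can be back-solved, assuming a two-sided test and rank-test efficiency 3/π = 0.955:

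- SD = 5.2 × √(22 × 0.955 / 2) / (1.960 + 0.842) = 5.2 × 3.241 / 2.802 ≈ 6.0.
- Forward check with SD 6: 2 × 2.802² × 36 / 5.2² = 20.9, and 20.9 / 0.955 = 21.9, rounded up to 22.

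The SD of 6 is therefore implied, not documented.

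**3. Size of the bias.** Suppose approach has no true effect. Let f be the share of SAVR patients with a concomitant operation, with none in the comparison arm, and g the added percentage fall in those patients. Both are assumed. The shift in the SAVR mean is f × g. The last column is the chance of p < 0.05 against SAVR with 22 per group: Φ(shift / s × 3.241 − 1.96), where s = √(36 + f(1 − f)g²/2) allows for the wider spread in the mixed arm.

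| f | g | shift | shift / 5.2 | s | chance |
|---|---|---|---|---|---|
| 20% | 5 | 1.0 | 19% | 6.16 | 8% |
| 20% | 10 | 2.0 | 38% | 6.63 | 16% |
| 30% | 10 | 3.0 | 58% | 6.82 | 30% |
| 50% | 10 | 5.0 | 96% | 6.96 | 64% |

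The nominal chance in that direction is 2.5%. The last column uses a normal approximation. Simulating the rank test itself (20,000 trials per row, normal errors, SD 5.98) gave somewhat lower values of 7%, 13%, 26% and 60%.

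**4. Can a covariate remove it?** Take 7 of 22 SAVR patients with a 10-point added fall and no arm effect.

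- Without an indicator, the expected SAVR–TAVR contrast is −(7/22) × 10 = −3.2.
- With an indicator, the SAVR term is estimated from the 15 SAVR patients without added surgery, and its expectation is 0.

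The indicator is estimable because concomitant surgery varies within the arm.

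**5. Price in precision.** A share of 20% to 50% is 4.4 to 11 of 22 SAVR patients. Power for the 5.2-point difference with n₁ left in SAVR, 22 in TAVR and SD 6 is Φ(5.2/6 × √(0.955 × 22n₁/(22 + n₁)) − 1.96):

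- n₁ = 22: 80%
- n₁ = 18: 76%
- n₁ = 15: 72%
- n₁ = 11: 63%

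Using the t distribution instead of the normal gives 78%, 74%, 69% and 60%.

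**The case against.** The strongest reply has four parts.

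- **Case mix.** The documents give no rate of combined operations in any arm and no figure for their effect on RV function. A reader might infer that such operations occur only in the SAVR arm. That is clinical expectation and no passage states it. This stands: concentration in SAVR and the direction of the bias are both assumptions.
- **Yardstick.** The 5.2 points are percentage change in RV strain, while Aim 2 concerns 3D RV EF. This also stands. The ratios in the table give scale only, and a range of 19% to 96% shows that the distortion could be small or large.
- **Adjustment.** A reader might infer that no covariate can correct for an operation found in one arm. Step 4 of the working shows otherwise, so restriction is not the only remedy.
- **Purpose.** The project is framed around the utility of 3D imaging, Aim 2 says only that the arms will be compared, and an all-comer arm can be a legitimate choice. This limits how strongly the point can be put, but it does not remove it. The plan does not say that an all-comer arm is intended, and a comparison labelled by approach will be read as one of approach.

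The figures in Section D could not be seen. If one carries a restriction, the written criteria still need to match it.

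**Conclusion.** The point holds in a limited form. On the written criteria, combined operations can enter any arm, and neither planned analysis accounts for them. If they are more common in the full-sternotomy arm and worsen RV function, the SAVR contrast is biased toward the expected finding. The illustrative size is 1 to 5 points of percentage change, for an assumed share of 20% to 50% and an assumed added fall of 5 to 10 points.

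A reader might go further and conclude that this gap alone prevents the trial from attributing a difference to approach, so that an isolated-AVR rule would restore attribution. The documents do not support that. No randomisation is described, and other differences between the arms would remain after restriction. The change removes one avoidable source of bias and should be made because it is cheap, but it does not settle causation.

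**What to change.** 1. Reconcile the mitral inclusion line in G.1 with the aortic population in the title, aims and Section D. This has to come first: if concomitant procedures were excluded while a mitral procedure is still required, no AVR patient would be eligible.
2. If enrolment has not begun, define all three arms as isolated aortic valve replacement, and add to G.1 an exclusion for any concomitant cardiac or aortic procedure planned with it.
3. If patients are already enrolled, record concomitant procedures from the medical record, which G.2 already lists as a data source. Make planned isolated AVR the main Aim 2 analysis set. Beside it, report an all-patient ANCOVA with a concomitant-procedure indicator, and describe the remaining patients separately. Base the classification on the planned operation, and set it before the arms are compared or label it as post hoc.
4. If an all-comer SAVR arm is intended, say so and word the Aim 2 conclusion accordingly.

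The cost is slower SAVR accrual, or about 4 to 11 of 22 SAVR patients outside the main set at a share of 20% to 50%. Power for that contrast would then fall from about 80% to between 76% and 60% at the implied SD of 6, unless replacements are enrolled. If all the combined operations are in SAVR, the indicator model has much the same precision, because its contrast rests on the same isolated patients.

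### No primary time point or contrast is named for 3D RV EF; 22 per group sizes SAVR versus TAVR at alpha 0.05, while the three-arm ANCOVA tests that pair under Bonferroni

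*Combined protocol and SAP*

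**What the plan says.** Section D (Research Design and Methods) gives the endpoint as "Primary outcome: 3D RV EF", with no time, change measure or pair of arms.

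Section A, aim 2, is to "Compare 3D RV EF between SAVR, mini AVR, TAVR". With three arms there are three pairs, and none is ranked above another. The timing table lists a baseline and two later assessments, "Post valve deployment RV (T#2)" and "Post chest closure RV (T#3)".

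Section E (Statistical analysis) states that the RV "indices will be analyzed using the Mann–Whitney U test (2 groups) or the analysis of covariance (ANCOVA) and pos-hoc pairwise comparisons with Bonferroni correction". It then gives covariates, including the baseline value of the index, "For ANCOVA of % change (Timing #3 from #1) in RV indices". That sentence covers all RV indices and is not labelled primary. The significance level is 0.05 throughout, and the Bonferroni family is not defined.

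Section E (Power analysis) uses RV strain changes of -25.2 for SAVR and -20.0 for TAVR, alpha 0.05 and "80% power for a Mann–Whitney U test", and arrives at 22 per group. Mini AVR does not enter the calculation.

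**The concern.** One primary outcome is not the same as one primary test. The plan does not say which comparison of 3D RV EF decides the study, and its two analysis routes err in opposite directions.

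- **ANCOVA route.** The three pairs share a Bonferroni correction, so the contrast behind the sample size is tested at a stricter level than the one it was sized for. The stated 80% then no longer describes the planned test.
- **Mann-Whitney route.** As the sentence is built, the correction attaches to the ANCOVA pairs. If the three arms are compared two at a time by Mann-Whitney, nothing corrects for having three comparisons.

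At stake are the power claim on one side and the false-positive rate for the primary outcome on the other. The choice between the routes is left open until the data are seen.

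**Working it through.** **Inputs from Section E.** Difference 25.2 − 20.0 = 5.2 percentage points; alpha 0.05; power 80%; Mann-Whitney; 22 per group.

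**Assumptions.** Two-sided tests; normal data; a Bonferroni family of three pairs; Mann-Whitney efficiency 3/π = 0.955 relative to the t-test.

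**1. The plan's own figure.** No SD is given, so 22 cannot be reproduced independently. It can only be inverted.
- Effective n per group = 22 × 0.955 = 21.0.
- Noncentrality = d × √(21.0/2). Power is 80% at d = 0.886, where the noncentrality is 2.87 on 40 degrees of freedom.
- Implied SD = 5.2/0.886 = 5.87.
- The result depends strongly on the SD. By the normal approximation, SDs of 5, 6, 7 and 8 give 16, 22, 31 and 40 per group.

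**2. Same contrast at 0.05/3 = 0.0167.**
- Mann-Whitney or two-group t: power about 65% (63% to 68% across one-sided, two-sided and efficiency variants). Restoring 80% needs about 30 per group (29 to 32).
- ANCOVA with the error pooled over three arms (66 − 3 = 63 degrees of freedom) and covariates explaining nothing: noncentrality = 0.886 × √(22/2) = 2.94. The critical value is 2.46 at 0.0167, giving power of about 68%. At 0.05 it is 2.00, giving about 82%.

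**3. Allowance for the plan's covariates.** If they explain a share R² of the variance, the noncentrality becomes 2.94/√(1 − R²).

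| R² | Noncentrality | Power at 0.0167 |
|---|---|---|
| 0 | 2.94 | 68% |
| 0.20 | 3.29 | 79% |
| 0.25 | 3.39 | 82% |

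The documents give no R².

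**4. False positives with no true differences, 22 per arm (simulation).**
- ANCOVA pairs with Bonferroni at T3: about 4.3% to 4.5%.
- Three uncorrected Mann-Whitney pairs at T3: about 12%. Three independent tests would give 1 − 0.95³ = 14.3%; the pairs share arms, so the figure is lower.
- The same three pairs at T2 as well: about 16% to 22%, depending on the correlation between the two changes. As a check, unrelated times would give 1 − 0.88² = 22.6%.

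**5. The alternatives (no covariate gain).**
- SAVR versus TAVR as the single contrast at 0.05: power about 82%, error about 5%.
- Closed test for three arms (global F at 0.05, then each pair at 0.05): error about 5%. Power for SAVR versus TAVR is about 72% if mini AVR lies midway, and about 78% to 79% if it equals either of the others.
- Both used side by side without gating: about 7.5% chance of at least one false claim.

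**The case against.** The strongest reply is that Section E already supplies most of what Section D leaves out. The ANCOVA sentence fixes a window (T3 from T1), a measure (percentage change), a model and baseline adjustment, and it covers 3D RV EF. The natural reading is that Mann-Whitney serves two-group comparisons and the corrected ANCOVA serves the three-arm aim. On that reading the familywise error at T3 is below 5%. This stands: the time-point gap lies in the endpoint definition and the missing label, not in every analysis.

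Two stronger inferences therefore fail.
- A reader might infer that following the plan gives roughly a one-in-five false-positive rate. That needs six uncorrected Mann-Whitney tests, half of them at T2, and Section E specifies no test at T2.
- A reader might infer that the study is underpowered. The covariates could recover the whole loss, and the sizing rests on RV strain, which is not a listed outcome. Power for 3D RV EF itself is unknown in either direction.

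It can also be said that the title and aims treat the three arms alike, so making SAVR versus TAVR primary is a scientific choice, and that Bonferroni is a valid method. Both are fair. Neither removes the mismatch: if all three pairs are equal, the sample size should have been calculated for a multiplicity-adjusted comparison, and it was not.

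**Conclusion.** The point holds as a mismatch between how the study was sized and how it will be tested, together with a missing primary label. The sized contrast has about 68% power under the planned Bonferroni-corrected ANCOVA if the covariates explain nothing. It returns to 80% only if they explain about 20% to 25% of the variance, for which the plan offers no support. The uncorrected Mann-Whitney reading gives about 12% familywise error at T3, and about 16% to 22% only if T2 is added.

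These figures assume two-sided tests, a family of three, normal data, equal arms of 22 with no losses, and an effect back-solved from the RV strain calculation. They show that the plan is inconsistent on its own terms. They do not show that its actual error rate is inflated or that its actual power for 3D RV EF is below 80%. The plan should be amended, and the amendment is cheap.

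**What to change.** 1. State that the primary analysis is the ANCOVA already described, applied to 3D RV EF: percentage change from T1 to T3, adjusted for the T1 value.
2. Name SAVR versus TAVR, the contrast the study was sized for, as the single primary contrast at two-sided 0.05.
3. Make T2, the mini AVR contrasts and all Mann-Whitney results secondary.
4. For the secondary three-arm comparison, replace Bonferroni with the closed test: global ANCOVA F at 0.05, then each pair at 0.05. With exactly three arms this holds the familywise error at 5%.
5. State that 5% is controlled separately for the primary test and for this secondary family, since together and without gating they give about 7.5%.

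If the investigators prefer to treat the three pairs equally, make the closed test primary and restate the power for SAVR versus TAVR as about 72% to 79% before any covariate gain.

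The cost is wording only, with no added patients or measurements. The price is that mini AVR and T2 findings cannot be presented as the primary result.

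### For demographic and nominal variables, the plan names two-group tests in a three-arm study and applies a rank test to unordered categories

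*Combined protocol and SAP*

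**What the plan says.** Section A (Specific Aims) defines three arms, SAVR, mini AVR and TAVR, and sets as its second aim "Compare 3D RV EF between SAVR, mini AVR, TAVR".

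Section E (Statistical analysis) gives the rule at issue: "Demographic data will be analyzed using the independent t-test, and the Mann–Whitney U test will be used for nominal variables". Just before it, the plan says how categorical data will be shown: "Categorical data are presented as frequencies and percentages according to the group". No chi-square test, Fisher's exact test, one-way ANOVA or Kruskal–Wallis test is named anywhere. For demographic and nominal variables the plan does not say which pairs of arms would be compared, or whether any correction would apply.

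The next sentence deals with the outcome measures separately: "RV echocardiographic indices will be analyzed using the Mann–Whitney U test (2 groups) or the analysis of covariance (ANCOVA"), followed by Bonferroni-corrected pairwise comparisons. The 0.05 significance level is stated once, for all tests.

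Gender is a named ANCOVA covariate. Race appears in Section F: "Any gender and race patients are included".

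**The concern.** The rule has two separate faults.

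1. **Data type.** Mann–Whitney compares the ranks of two samples. A nominal variable has no ranks until someone assigns numbers to its categories. With three or more categories, different numberings can give different p-values from the same table.
2. **Number of groups.** The independent t-test and Mann–Whitney each compare two groups. With three arms, either only some pairs are tested or all three are, and the plan states neither the pairs nor a multiplicity rule.

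The available text describes no randomisation, and the arms are different procedures. A reader will use the baseline table to judge whether the arms are comparable. A p-value that moves with the category numbering, or that comes from an unspecified set of pairwise tests, does not help with that judgement.

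**Working it through.** **Inputs.** Three arms (Section A). Level 0.05 and 22 patients per group (Section E). The category counts are assumptions made for illustration, because the plan gives none.

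**The plan's own figure.** The only design number is 22 per group, for RV strain changes of −25.2 and −20.0, a difference of 5.2 points. No SD is given, so it cannot be reproduced. Under a two-sided normal approximation it implies an SD of about 6.0 to 6.15. It is used here only as an arm size, and the point does not depend on it.

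**Step 1: three-category variable, two arms of 22.** Assume categories a/b/c with counts 14/2/6 in one arm and 6/10/6 in the other. The totals are 20/12/12, so the expected counts are 10/6/6 in each arm.

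*Chi-square* = 2 × (4²/10) + 2 × (4²/6) + 0 = 3.20 + 5.33 = 8.53 on 2 df, p = 0.014. This does not depend on labels or order.

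*Mann–Whitney* (normal approximation, tie-corrected, no continuity correction):

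- Variance of U = (22 × 22/12) × [45 − (7980 + 1716 + 1716)/(44 × 43)] = 40.33 × 38.97 = 1571.7, so the SD is 39.65.
- The expected U is 22 × 22/2 = 242.
- U = (rank sum of the first arm) − 22 × 23/2 = (rank sum) − 253.

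| Category order | Mid-ranks, in that order | Rank sum, first arm | U | z | p |
|---|---|---|---|---|---|
| a, b, c | 10.5, 26.5, 38.5 | 147 + 53 + 231 = 431 | 178 | −1.61 | 0.106 |
| b, a, c | 6.5, 22.5, 38.5 | 13 + 315 + 231 = 559 | 306 | +1.61 | 0.106 |
| a, c, b | 10.5, 26.5, 38.5 | 147 + 159 + 77 = 383 | 130 | −2.82 | 0.0047 |

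Reversing an order changes only the sign of z, so these three rows cover all six codings: four give 0.106 and two give 0.0047. The same data fall on either side of 0.05 by numbering alone.

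**Step 2: binary variable.** Assume 14/8 and 8/14. Mann–Whitney gives p = 0.074 under both codings, against 0.070 for the uncorrected chi-square. The coding fault disappears with two categories. The two-group fault remains.

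**Step 3: three arms, all pairs tested at 0.05 without correction.** If the three tests were independent, the chance of at least one false difference would be 1 − 0.95³ = 0.143. They are not independent, because each arm enters two pairs. A simulation under the null (normal data, three arms of 22, 100,000 runs) gives:

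| Procedure | At least one p < 0.05, or global p < 0.05 |
|---|---|
| Three uncorrected t-tests | 12.2% |
| Bonferroni-corrected t-tests | 4.4% |
| One-way ANOVA | 5.0% |

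**The case against.** **Nominal may be a slip for non-normal.** A t-test paired with Mann–Whitney, shortly after a sentence on mean and SD or median and IQR, reads naturally as normal versus non-normal data. That is plausible, though the text does not say so. On that reading the coding problem goes away. However, both tests would still be two-group tests, and categorical data would have no named test at all. The sentence needs correcting either way.

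**The table shows any imbalance without a p-value.** Counts and percentages by arm are already planned, and a large imbalance would be visible in them. The ANCOVA covariates are fixed in advance (age, gender, norepinephrine equivalent, CVP and the baseline index), so no stated rule lets baseline p-values choose the adjustment. This stands, and it limits the harm. It does not make the named tests suitable.

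**Stronger readings that the documents do not support.**

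- A reader might infer that nothing in the plan covers all three arms. The ANCOVA with Bonferroni comparisons can do so for the RV indices; the gap concerns demographic and nominal variables only.
- A reader might infer that every nominal p-value depends on coding. Step 2 shows that binary variables do not. Gender is the only categorical covariate named in the analysis, and race appears only in the inclusion statement.
- A reader might infer that Mann–Whitney on nominal data creates false imbalances. With a coding fixed in advance it keeps roughly its nominal error rate when the arms do not differ; a poor coding costs power. The 12% comes from uncorrected pairwise testing, which the plan leaves open but does not prescribe.
- More dramatic examples can be built. With 10/2/10 against 2/18/2, Mann–Whitney gives p = 1.00 or 0.00001 depending on the coding. That split is symmetric by construction and should not be taken as the expected size of the problem.

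**Conclusion.** The point holds for demographic and nominal variables. The stated tests do not match the number of arms, and Mann–Whitney does not suit nominal variables with three or more categories. In a moderate assumed example, coding alone moves p between about 0.005 and 0.11, against a chi-square value of 0.014. The false-difference rate is about 12% per variable, on the assumption that all three pairs are tested without correction in arms of 22.

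A reader might take this as a threat to the trial's main result. The documents do not support that: the RV indices have their own analysis, and neither the primary 3D RV EF comparison nor the sample size relies on this sentence. What is affected is the baseline comparison of the arms. That is worth correcting, because the available text describes no randomisation.

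**What to change.** Replace the sentence in Section E. For nominal variables, use a chi-square test across the three arms, or Fisher's exact test where expected counts are small. For continuous demographic variables, use one-way ANOVA, or Kruskal–Wallis where the distribution is not normal. If non-normal was the intended word, correct it and still name a test for categorical data.

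Pairwise standardised mean differences are an optional addition that shows the size of any imbalance directly.

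The cost is one sentence in the plan. No patients, data or procedures are added, and the sample size does not change.
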